1.0 Objectives

We will leverage increasingly available technologies to impart a Universal Medication Schedule (UMS) in primary care to help patients living with diabetes safely use and adhere to complex drug regimens. We will conduct a 3-arm, multi-site trial to:

1.1 Specific Aims:

1. Test the effectiveness of the UMS, and UMS + SMS text reminder strategies compared to usual care.
2. Determine if the effects of these UMS strategies vary by patients' literacy skills and language.
3. Using mixed methods, Evaluate the fidelity of the two strategies and explore patient, staff, physician, and health system factors influencing the interventions.
4. Assess the costs required to deliver either intervention from a health system perspective.

1.2 Hypotheses:

1. Compared to usual care, patients receiving the UMS or UMS+SMS text reminder strategies will demonstrate a better understanding of how to safely dose their Rx regimen
2. Compared to usual care, patients receiving the UMS or UMS+SMS text reminder strategies will when possible, take their Rx regimen fewer times per day
3. Compared to usual care, patients receiving the UMS or UMS+SMS text reminder strategies will have greater adherence to their Rx regimen
4. Compared to the UMS only arm, patients receiving the UMS+SMS strategy will have greater adherence to their Rx regimen.
5. The intervention effects will be greater among those with limited literacy and English proficiency.

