based on the distribution of the outcome variable. The GLMMs will include random provider effects and fixed binary variables for SMS text reminder and EHR to denote the intervention groups and the usual care group (H1-4). We will include a fixed indicator variable for clinic in the GLMMs and any potential confounding covariates as noted above. Analyses will be performed using PROC GLMMIX in SAS (v.9.3) and lme4 package in R. Since understanding and adherence will be assessed for each medication, 2-level GLMM will be used with medications nested in participants. We will first test for differences in the outcomes between the EHR group and usual care (H1-3), followed by comparisons between EHR+SMS vs. usual care, and EHR vs. EHR+SMS to determine additional benefits of SMS texting (H4) by constructing contrasts.

Aim 2

We will include both literacy-by-arm and language-by-arm fixed interaction terms in the above GLMMs for all outcomes. We will use the corresponding model type III tests for fixed effects to determine significance of terms, and construct appropriate contrasts for pairwise comparisons for each literacy level and each language.

Aim 3

We will determine the extent to which the interventions were implemented as planned (a process evaluation) across each site and for all three study arms, in order to optimize the intervention for future dissemination opportunities.

Mixed methods will be employed using a convergent parallel design to obtain data on intervention implementation.

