interventions will be estimated relative to usual care from the perspective of NMHC, NM Regional Medical Group, and MSMC practices implementing these processes and tools. First, we will document the initial costs associated with programming the EHR tools at a new site, following the code and standard operating manual guidance from Aim 3. The primary costs of running these UMS technologies in the EHR arm involves the limited expenses around printing the EHR tools (printer ink, paper, staff time) as a result of generating new Rx information with after-visit summaries. SMS monthly costs will be easily documented from EZText invoices as well as usage. However, we will include estimates for programming maintenance for Epic EHR, and will test the sensitivity of results to changes in the maintenance requirements in terms of programmer hours, calculated per site. We also will separately track development costs for software and other programming requirements based on programmer hours. Staff/programmer costs will be measured using tracked time spent on the intervention and wage estimates. We will test the sensitivity of operational costs to different assumptions about the potential use of variable staff using different salaries but assuming the same proficiency in terms of time required. Further, we will assess the sensitivity of estimates to different proficiency levels that could arise from learning by doing.

Exploratory Analyses. We will repeat all GLMM analyses described for Aim 1 to explore whether differences in interventions vary by relevant covariates representing patient and regimen characteristics known to impact outcomes, specifically adherence. Interaction terms will be included in models accordingly. As adherence has its many measurement challenges, experts recommend triangulating with multiple measures. We will compare results across each adherence measure (ASK-12, 24-hour recall, pill count) and create a general estimate of adherence via single factor score using maximum likelihood estimation. Exploratory analyses will examine HbA1c and blood pressure from baseline to 6 months, although power may be limited. Additionally, we will construct marginal models for all primary and secondary outcomes using generalized estimating equations (GEE) in a process similar to those described for the GLMMs. The purpose is to obtain population-averaged estimates of any differences in outcomes across arms vs. estimates at participant level.

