20.0 Resources Available

20.1 The research team is comprised of 3 PhD level researchers, 5 Physician-researchers, 1 master's degree level researcher, 2 project managers, and 4 bilingual research assistants (all with experience on similar projects). The co-PIs represent two academic institutions with proven track records in health literacy, medication safety and adherence, and the use of health technologies. All team members have extensive knowledge on health literacy in the context of medication management and health technologies. Co-Investigators on this project include the Lead Technical Informaticist of Epic EMR Clinical Transformation Group, Mount Sinai Health System, and the Director of the Health Literacy and Learning Program (HeLP), which seeks to advance the study of limited health literacy and interventions that could improve one's ability to obtain, process, and understand basic information needed to make appropriate health decisions. The investigators have successfully collaborated on numerous previous projects.

Both site project managers have 5 years of experience managing complex research studies and supervising research staff. The research assistants receive extensive training on research methods, interviewing techniques and the consent process.

20.2 NMHC: The GIM clinic of NMHC has >20,000 active patients (patients with two or more office visits in the past 18 months), of whom nearly 3,000 are living with type 2 diabetes. The practice serves a diverse patient population (30% African-American, 10% Latino) and represents the entire spectrum of socioeconomic status. The practice

Regimen Education and Messaging in Diabetes (REMinD)

is comprised of 4 clinical ‘pods’ and employs ~40 attending physicians and 77 residents.

Northwestern Medicine Regional Medical Group: The GIM clinic of NM Regional Medical Group has over 74,000 active patients. The GIM practice within the Regional Medical Group is comprised of 14 clinics and employs ~168 physicians.

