MSMC: The Internal Medicine Associates of Mt. Sinai (IMA) is the large, hospital-based general medicine practice for the Mt. Sinai Medical Center. It is comprised of 4 individual practice firms and employs ~40 full-time attending physicians, 3 general medicine fellows, and 140 residents. The practice has almost 24,000 patients; 5,000 have diabetes. IMA is located in East Harlem, NY and the demographics of its patients reflect the diversity of the surrounding communities. Both NMHC and MSMC use the Epic EHR platform. With these sites combined, we have already identified via each sites’ enterprise data warehouse (EDW) 7,837 eligible patients for the study.

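### Aim 2 has no site-by-arm term: if Spanish-speaking share and arm effect both differ between the two sites, part of the site difference is credited to language, or masks it

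*Combined protocol and SAP*

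**What the plan says.** Section 1.2 states hypothesis 5: "The intervention effects will be greater among those with limited literacy and English proficiency". Section 11.1 (Aim 2) tests it this way: "We will include both literacy-by-arm and language-by-arm fixed interaction terms in the above GLMMs for all outcomes".

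The models referred to are those of Aim 1. There, "The GLMMs will include random provider effects and fixed binary variables for SMS text reminder and EHR", and clinic comes in as follows: "We will include a fixed indicator variable for clinic in the GLMMs and any potential confounding covariates as noted above". No clinic-by-arm or site-by-arm term is named.

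No other planned analysis supplies one. The exploratory interactions in section 11.1 ask whether differences between interventions "vary by relevant covariates representing patient and regimen characteristics known to impact outcomes, specifically adherence"; site is not among them. Aim 3 looks at implementation at each site, but it is a process evaluation that does not feed into the Aim 2 models.

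On who comes from where, section 4.1 plans about 450 patients per site, and section 3.1 admits English and Spanish speakers without a quota by site. Section 20.2 gives 10% Latino for one Northwestern practice (NMHC) and no ethnicity figure for the Regional Medical Group. For Mt. Sinai it gives no percentage: "IMA is located in East Harlem, NY and the demographics of its patients reflect the diversity of the surrounding communities".

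**The concern.** A clinic main effect lets adherence be higher or lower at one clinic than at another. It does not let the intervention work better at one site than at the other. In the Aim 2 model the arm effect may vary only with literacy and language. If language mix also differs by site, the language-by-arm coefficient stands in, in part, for the missing site-by-arm term.

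At stake is the interpretation of hypothesis 5. The language half could appear supported because one site delivered the tools better, or a real language difference could be masked; the direction depends on which site responds better. The literacy half is exposed only if literacy also differs by site, which the documents do not report.

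**Working it through.** **The plan's own figure.** There is none for this point. The power statement in section 11.2 concerns pairwise arm differences, not an interaction.

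**Inputs from the documents.** 450 patients per site (section 4.1); 240 per arm analysed at six months (section 11.1), taken here as 120 per site per arm; arms balanced within site, because randomization is stratified by clinic (section 11.1) or by health center (section 9.2.1).

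**Assumptions.** Spanish-speaking shares are not given, so a range is tried. The outcome is binary with SD 0.5 on the risk-difference scale. One pairwise arm contrast is tested two-sided at a nominal 5%, with no true language effect. Literacy-by-arm is left out for simplicity.

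**Step 1: share of a site difference that loads onto language.** With arms balanced within site and site-by-arm omitted,

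share = P(Mt. Sinai | Spanish) − P(Mt. Sinai | English).

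Example, 2% at Northwestern and 50% at Mt. Sinai: Spanish speakers number 9 and 225, English speakers 441 and 225. Share = 225/234 − 225/666 = 0.962 − 0.338 = 0.62.

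**Step 2: standard error of the language interaction without site-by-arm.** With p the overall Spanish share,

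SE = √[2 × 0.25 / (240 × p(1 − p))].

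At 2%/50%, p = 234/900 = 0.26, so SE = √[0.5 / (240 × 0.1924)] = 0.104.

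**Step 3: error and rejection rate.** Error = share × site difference in arm effect. With z = error/SE, rejection = Φ(z − 1.96) + Φ(−z − 1.96). At 2%/50% and a 10-point site difference, error = 0.062, z = 0.60 and rejection = 9%.

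**Step 4: cost of adding site-by-arm.** The variance rises by 1/(1 − φ²), with φ the correlation between language and site. At 2%/50%, φ = 0.547, the factor is 1.43 and the SE is √1.43 = 1.195 times as large.

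| Spanish share, Northwestern / Mt. Sinai (assumed) | Share loaded on language | Error at 10-point site difference | Rejection at 10 points | Rejection at 20 points | SE increase with site-by-arm |
|---|---|---|---|---|---|
| equal | 0% | 0 | 5% | 5% | 0% |
| 10% / 20% | 20% | 2.0 points | 5% | 6% | 1% |
| 5% / 30% | 43% | 4.3 points | 6.5% | 11% | 6% |
| 5% / 50% | 56% | 5.6 points | 9% | 20% | 16% |
| 2% / 50% | 62% | 6.2 points | 9% | 22% | about 20% |

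**Step 5: checks.** A simulation at 5%/30% with a 14-point site difference and no language effect gave a mean language interaction of 0.07 without site-by-arm (formula: 0.433 × 0.14 = 0.061) and about 0.01 with it. The random provider intercept gives little protection: with 3 patients per provider, the 5%/30% share stays at 0.43 at an ICC of 0.01 and falls only to 0.40 at 0.05.

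**Step 6: does the extra term improve accuracy?** Root mean squared error is √(SE² + error²) without the term and the inflated SE with it. At a 10-point site difference: 0.129 versus 0.129 (10%/20%) and 0.121 versus 0.124 (2%/50%). At a 20-point difference and 2%/50%: √(0.104² + 0.125²) = 0.162 versus 0.124.

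**The case against.** The strongest reply is that both conditions are undocumented. A reader might infer from the East Harlem location and the 10% Latino figure that Spanish speakers are concentrated at Mt. Sinai. The 10% is ethnicity, not language, and describes one Northwestern practice. Nothing is given for the Regional Medical Group, which is also a recruitment source, or for Mt. Sinai. With equal shares the error is exactly zero.

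A reader might also infer that the tools work differently by site because each site has its own EHR build, or because residents are 140 of the 183 clinicians listed for Mt. Sinai against 77 of about 285 for Northwestern. The documents do not describe separate builds: NMHC and Mt. Sinai both use Epic (section 20.2), and Mt. Sinai follows identical procedures (section 6.1). The resident counts describe employed clinicians, not those enrolled. The most the text offers is the field-notes plan in section 9.9, which expects that changes in staffing, workflow or EHR could alter delivery. That makes a site difference conceivable, not shown.

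It can further be said that Aim 2 asks only whether effects vary by language, that language is not randomized, and that other correlated characteristics could equally modify the effect. This is fair: adding site does not make the interaction causal. The language-by-arm standard error is also about 0.10 to 0.13 in the table's scenarios, so a shift of 2 to 6 points is small beside it, and step 6 shows no accuracy gain from the extra term at a 10-point site difference.

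These arguments stand against replacing the planned model. They do not remove the gap: nothing planned would show whether an apparent language difference is partly a site difference.

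**Conclusion.** The point holds as a conditional weakness in Aim 2. It needs two things together: a language mix that differs by site and an arm effect that differs by site. Over the assumed shares, 0% to 62% of a site difference in effect would go to the language interaction. For a 10-point site difference that is an error of 0 to 6 points and a rejection rate of 5% to 9%. The 22% figure needs both a 20-point site difference, which exceeds the 14-point arm effect used for power in section 11.2, and the most extreme shares tried.

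Three stronger conclusions should not be drawn. The whole of a site difference is not credited to language, only the fraction in step 1. The Aim 1 arm comparisons are not confounded by site, because stratified randomization balances arms within site. Nor does the calculation show bias in the literacy contrasts; it did not cover them.

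This supports a pre-specified sensitivity analysis, not a change to the model of record.

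**What to change.** Keep the Aim 2 model as planned, and add three things to section 11.1:

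1. A table of language by site and arm.
2. A pre-specified sensitivity model that adds a site-by-arm interaction beside language-by-arm and literacy-by-arm. Site should have two levels (Northwestern, Mt. Sinai), not one per clinic, so the term uses 2 df with three arms.
3. Language-by-arm estimates within each site, shown descriptively.

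State that a difference in benefit will be attributed to language only if the language-by-arm estimate is similar in the sensitivity model.

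The cost is one more analysis on data already held. In it, the standard error of the language interaction is about 0% to 20% larger over the shares assumed above.

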2.0 Background

2.1 The Challenge of Managing Complex Drug Regimens:

In ambulatory care, patients assume primary responsibility for safely and appropriately administering Rx regimens. Yet the expectations placed on patients by the healthcare system for medication-related tasks are considerable. In order for patients to gain the benefits of drug therapy while minimizing risks of adverse drug events (ADEs), they must: 1) have a functional understanding of medications and their proper dosing, 2) consolidate their regimen to the most efficient daily schedule, 3) problem-solve around regimen use as changes occur, and 4) continue the behaviors

Regimen Education and Messaging in Diabetes (REMinD)

over time. Studies have repeatedly documented that patients have problems performing these routine tasks. This is alarming, as adults are being prescribed increasingly complex medication regimens. Over the past decade, the percentage of Americans taking ≥ 5 Rx drugs daily has doubled to nearly 40% of older adults. While long-term adherence is essential to reap health benefits, all forms of non-adherence - failure to fill new prescriptions, incomplete use, and premature discontinuation - are common. Non-adherence has been linked to greater morbidity and mortality from chronic conditions. Complex drug regimens also raise the risk for errors and ADEs, many of which are preventable or ameliorable. Nearly 10 million outpatient physician visits and 4 million emergency department admissions are attributed to ADEs or side effects annually. These are more likely to occur in primary vs. specialty care, among older patients, and those with multi-morbidity.

The Case of Type 2 Diabetes. The increasing number of individuals living with type 2 diabetes (estimated at 10% of the U.S. adult population) must contend with extended duration, multi-drug regimens to manage the disease. These regimens often require frequent dosage changes and have formidable potential side effects (e.g. hypoglycemia) that may intentionally – or unintentionally – distract one from proper medication use. Yet these patients are also likely to have comorbid conditions, such as hypertension and hyperlipidemia that require additional medications, further complicating daily Rx regimen schedules. In a study of 13,365 type 2 diabetic adults, Chen et al. classified 38% as having moderate to major polypharmacy concerns. A significant, gradient association was found between increasing polypharmacy and higher rates of non-adherence to oral anti-diabetic drugs (measured via refill, proportion of days covered).

Age, Literacy, and Language as Risk Factors. Older age poses a significant risk for medication safety and adherence concerns. The prevalence of multi-morbidity increases with age; approximately 17% of younger adults ages 20-39 live with 2 or more chronic conditions compared to a third of middle-aged adults (40-59), and nearly two thirds of individuals over 60 years old. This, in turn, often translates to a greater number of prescribed medications. As part of the aging process, the challenge of managing complex Rx regimens is made ever more difficult by higher rates of cognitive decline and limited health literacy.

Numerous studies have found limited literacy skills to be significantly associated with patients' poorer recall of medication names and indications, inadequate understanding and demonstrated use of Rx instructions and precautions.^{5,6,32-37} Our team also found that patients, especially those with lower literacy, may overcomplicate multi-drug regimens by taking medicine more times a day than necessary.⁴ While studies are inconclusive as to whether lower literacy is associated with non-adherence,³⁸⁻⁴¹ evidence clearly suggests lower literate patients are more likely to misunderstand Rx instructions, putting them at greater risk.^{7,42}

In addition, limited English proficiency (LEP) presents a formidable barrier in healthcare.⁴³⁻⁴⁸ Interpreters are rarely available to aid physicians and pharmacists in

Regimen Education and Messaging in Diabetes (REMinD)

counseling LEP patients on safe R_x use, instructions are frequently unavailable in non-English languages, and multilingual materials are often inaccurate and poorly translated.⁴⁹⁻⁵² These barriers have a deleterious effect on LEP patients' R_x use.⁵³⁻⁵⁵ Wilson et al. found among 1200 LEP adults, half had difficulties interpreting R_x instructions and 16% reported an ADE.⁵⁵ Similarly, Sleath et al. found that 58% of LEP adults misinterpret English R_x instructions.⁵⁶

Health System Barriers. Individual barriers such as older age, limited literacy, and LEP are exacerbated by health system barriers.⁵⁷ Multiple studies have shown physicians often fail to discuss with patients basic information around the safe use of prescribed medicines, let alone other relevant concerns (i.e. cost of medications).⁵⁸⁻⁶² Furthermore, print R_x information is rarely distributed at the point of prescribing. Evidence also suggests that pharmacists equally fail to counsel patients on safe and appropriate R_x use.^{58,60,61} While print materials (R_x labels, warning stickers, Medication Guides, patient leaflets) are provided by pharmacies, most are poorly written and confusing.⁶³⁻⁶⁶ In addition, considerable variability has been identified across this process.⁶⁷⁻⁶⁹ Bailey et al. found R_x instructions written by physicians to be highly variable;⁶⁸ [name] et al. reviewed R_x instructions printed by multiple pharmacies and also found that pharmacy translations often deviated from physicians' instructions.⁶⁹ *Variable, poor quality physician prescriptions and pharmacy translations and lack of appropriate counseling complicate the task of organizing and properly dosing multi-drug regimens.*

2.2 An Evidence-Based Solution: A Universal Medication Schedule:

The IOM 2008 report *Standardizing Medication Labels* recognized the need to set standards for prescribing and dispensing practices to promote safe and accurate medication use.⁷⁰ Members of our research team ([name], [name]) presented the UMS concept in this report. As nearly 90% of prescriptions are taken 4 times a day or less, the UMS specifically proposed to establish 4 standard time intervals (morning, noon, evening, bedtime) for the prescribing and dispensing of medicine. This would remove current variability in the way prescriptions are written by physicians and transcribed by pharmacists.⁶⁷⁻⁶⁹ All prescriptions would instruct patients to take their medicine at one or more of these specified times; this would be described in a single, standardized fashion (**Figure 1**). UMS instructions also use health literacy best practices, like simplified text, numeric characters instead of words to detail dose (1 instead of 'one'), and carriage returns (placing each dose on a separate line) to clearly identify every time a medicine is to be taken.⁴

Figure 1. The Universal Medication Schedule (UMS)

Take	1 pill in the morning	
Take	1 pill in the morning 1 pill in the evening	⌚ Morning: 6-8 am
Take	1 pill in the morning 1 pill at noon 1 pill in the evening	⌚ Noon: 11-1 pm
Take	1 pill in the morning 1 pill at noon 1 pill in the evening 1 pill at bedtime	⌚ Evening: 4-6 pm ⌚ Bedtime: 9-11 pm

Regimen Education and Messaging in Diabetes (REMinD)

There is strong evidence supporting the UMS.^{4,70-77} Among a multi-site sample of 500 primary care patients, [name] et al. found those receiving UMS instructions versus a current standard were 33% more likely to accurately interpret Rx instructions.⁷² Lower literate adults were more likely to correctly comprehend the UMS instructions. These findings were replicated among 94 patients in Cork, Ireland, and also among 203 LEP patients in Chicago and San Francisco.^{73,74,78} Earlier studies also found the use of more explicit time intervals, such as those used in the UMS approach, improved patient understanding and reduced medication errors.^{72,79}

Our team recently completed a clinical trial testing the UMS as an embedded standard in pharmacy practice [R01HS017687; R01HS016435]. 845 English and Spanish-speaking, low-income patients with type 2 diabetes and hypertension being cared for by one of 8 community health centers in the Washington D.C. area received reduced-cost medications from a collaborating non-profit, central-fill pharmacy. Patients were randomized to receive their bundled medications with UMS label instructions or a current standard modeled after a leading national pharmacy chain (no orientation to UMS provided). Over 9 months, English and Spanish-speaking patients improved their proper use of multi-drug regimens (OR 1.98, 95% CI 1.02-3.85) and had a near 2-fold increased adherence rate measured by pill count (OR 0.58, 95% CI 0.35-0.98). Exploratory analyses found a non-significant trend for glycemic control (tight control (HbA1c <7.0%: 56% (UMS) vs. 46% (Standard), p=0.15). As with prior studies, these benefits were greatest for lower literate adults and those taking >5 Rx drugs. *The IOM has repeatedly highlighted the UMS; the US Pharmacopeia, American College of Physicians and National Council for Prescription Drug Programs recommend it as a standard; and California passed legislation in 2011 stating the UMS as a best practice for Rx labeling, also supported by the National Board of Pharmacy.*^{70,80,81}

2.3 Shifting Upstream: Implementing the UMS at Prescribing vs. Dispensing Medication:

The above AHRQ/NIH-funded trials revealed several obstacles: 1) over half of patients routinely use multiple pharmacies resulting in their continued receipt of variable Rx label instructions, 2) imparting the UMS only on drug labels was not a sufficient signal to patients to consolidate multi-drug regimens, 3) patients need comprehensive views of the UMS applied to their entire Rx regimen vs. individual Rx labels only, and 4) additional reminders may be beneficial to reinforce UMS prescribing after medical encounters, helping patients remember and simplify daily Rx use, and support adherence. Both pharmacy and patients expressed a need for improved, plain language Rx information that provides general knowledge to support safe Rx use. Our proposal is based on evidence from the field, extensive experience with EHRs, mobile technology, and funded development work [R18HS17220, R21CA132771, R01NR011300, R01NR012745, U19HS021093, California Endowment, California Healthcare Foundation]. We will shift the implementation of the UMS to primary care, leveraging technologies that are increasingly prevalent per federal mandates (Health Information Technology for Economic and Clinical Health

Regimen Education and Messaging in Diabetes (REMinD)

(HITECH) Act), particularly among community health centers.⁸² We respond to the Office of the National Coordinator ‘Meaningful Use’ criteria by leveraging an EHR to impart standard, patient-centered information supporting safe Rx use.⁸³

2.4 Leveraging Increasingly Available Technologies to Support Medication Use:

Technological solutions are increasingly available that can be leveraged to help patients learn how to safely and appropriately take prescribed drugs that are not cost-prohibitive, such as EHRs and SMS text messaging.^{82,84-86}

‘Meaningful Use’ of EHRs. Now in the second stage of the Office of the National Coordinator (ONC) ‘Meaningful Use’ criteria that establishes incentives and directives for leveraging EHRs in practice, the proposed UMS interventions are directly responsive to the upcoming third stage criteria (2016) that seek ways that physician practices can use their EHR to improve: 1) quality, safety, and efficiency leading to improved health outcomes, and 2) patient access to self-management tools.⁸³ Our team has successfully field tested the UMS strategy at two academic centers using different EHR platforms (EpicCare: R18HS17220, R21CA132771; Cerner: U19HS021093).⁸⁴ This included: 1) UMS-mapped standard physician instructions (a.k.a. ‘sigs’) that were e-prescribed to pharmacies (Epic only), 2) plain language medication information sheets (‘MedSheets’) incorporating the UMS sig given to patients upon checkout, and 3) a redesigned EHR medication list (‘MedList’) that organized a patient’s entire Rx regimen according to UMS intervals (Cerner only). All of these tools were co-developed by physicians, nurse practitioners, nurses, and clinic administrative staff to ensure all would not negatively impact clinic workflow and efficiency. The intervention includes UMS sigs and decision support tools for asthma, which have been developed, vetted by providers, and successfully piloted at Mt. Sinai.

Mobile Technologies to Promote Health Behavior Change. While EHRs can be leveraged to provide tools to support appropriate medication use in primary care, additional measures may be necessary to promote safe medication use outside of healthcare settings.^{84,87} Mobile technologies, specifically SMS text messages, have been used to provide health-centered messages to patients in their daily lives.⁸⁸⁻⁹¹ Recent estimates indicate mobile technologies are useful tools for reaching low-income populations and racial/ethnic minorities; 92% of African-American and Latino adults own cell phones.⁹² Text messaging capabilities are also commonly used; 81% of cell phone users send or receive text messages.⁹² *While use of this technology is more common among younger adults, the number of older adult cell phone (even smart phone and tablet) users is increasing exponentially (89% ages 50-64; 77% ≥65), including those who actively receive and send text messages.⁹²*

Multiple studies have evaluated text messaging as a means to change behavior.^{87,88,93} Cole-Lewis & Kershaw evaluated 12 interventions that utilized text messaging as a platform for disease management or prevention.⁸⁸ Eight studies reported positive changes in among individuals receiving text messages for outcomes including weight

Regimen Education and Messaging in Diabetes (REMinD)

loss, smoking cessation, blood glucose monitoring and hemoglobin A1c. Recent studies have found text reminders increased Rx adherence, yet causal mechanisms and 'best practices' remain unclear.^{94,95}

